## **5.4. Administration**

All investigational products will be administered on an outpatient basis.

### **5.4.1. Avelumab**

The Drug Administration Instructions within the IP Manual contains specific instructions for avelumab dose calculation, reconstitution, preparation of the infusion fluid, and administration.

Avelumab will be administered on Days 1, 15 and 29 of each cycle after all procedures/assessments have been completed as described in the [Schedule of Activities](#) table. Avelumab may be administered up to 3 days before or after the scheduled Day 1 of each dose.

Avelumab will be administered as a 1-hour IV infusion once every 2 weeks. In order to mitigate infusion-related reactions, a premedication with an antihistamine and with paracetamol (acetaminophen) to be administered approximately 30 to 60 minutes prior to each dose of avelumab is mandatory (for example, 25-50 mg diphenhydramine and 500-650 mg paracetamol [acetaminophen] IV or oral equivalent). This may be modified based on local treatment standards and guidelines, as appropriate. As per Amendment 8, premedication is no longer required unless clinically indicated by the presence/severity of prior infusion reactions. Sites should make every effort to target infusion timing to be as close to 1 hour as possible. However, given the variability of infusion pumps from site to site, time windows of -10 minutes and +20 minutes is permitted (ie, infusion time is 60 minutes: -10 min/+20 min). The exact duration of infusion should be recorded in both source documents and Case Report Form (CRF). Possible modifications of the infusion rate for the management of infusion-related reactions are described in [Section 5.4.6.6](#).

The dose amount required to prepare the avelumab infusion solution will be based on the patient's weight in kilograms (kg). All patients should be weighed within 3 days prior to dosing for every infusion. If the patient experienced either a weight loss or gain >10% compared to the weight used to calculate the prior dose, the amount of study drug required for preparation and administration for the current treatment must be recalculated using this most recent weight obtained. For weight changes <10% compared to the weight used to calculate the prior dose, the decision on whether to recalculate the avelumab dose will be made in accordance with local practices. Avelumab dose reduction for toxicity management is not permitted, however next administration may be omitted due to persisting toxicity as described in Table 3 and [Section 5.4.6](#).

Patients experiencing toxicity may require treatment adjustment or discontinuation according to the guidelines specified in Table 3.

#### **5.4.2. Axitinib**

Axitinib will be administered orally BID at approximately the same time in the morning and evening on a continuous dosing schedule, ie, without a break in dosing in the absence of drug-related toxicity (see [Section 5.4.6](#)). Axitinib tablets are to be taken approximately 12 hours apart and may be administered without regard to meals. Tablets must not be crushed, split, or dissolved, and patients should be instructed to swallow the study medication whole without manipulation or chewing of the medication prior to swallowing.

A dosing card will be provided to the patients to provide guidance for the correct use of axitinib.

Patients must be instructed that if they miss a dose or vomit anytime after taking a dose, they must not "make it up" with an extra dose, but instead resume subsequent doses as prescribed.

Any missed dose may be taken late, up to 3 hours before the next scheduled dose of that day, otherwise, it should be skipped and dosing resumed with subsequent doses as prescribed. Patient must be instructed to record all doses (missed or vomited doses or extra doses) in a dosing diary supplied by the site. If doses are missed or vomited or if an extra dose is taken, this must be indicated in the source documents and CRFs.

Patients experiencing toxicity may require treatment adjustment or discontinuation according to the guidelines specified in Table 1 and Table 3.

#### **5.4.3. Sunitinib**

Sunitinib will be administered orally QD at approximately the same time daily continuously for 4 consecutive weeks followed by a 2-week off-treatment period (Schedule 4/2 in 6-week cycles), Sunitinib capsules are to be taken daily and may be administered without regard to meals. Capsules must not be opened, split, or dissolved, and patients should be instructed to swallow the study medication whole without manipulation or chewing of the medication prior to swallowing.

A dosing card will be provided to the patients to provide guidance for the correct use of sunitinib.

Patients must be instructed that if they miss a dose or vomit anytime after taking a dose, they must not “make it up” with an extra dose, but instead resume subsequent doses as prescribed. Any missed dose may be taken late in the same day, otherwise, it should be skipped and dosing resumed with subsequent doses as prescribed. Patient must be instructed to record all doses (missed or vomited doses or extra doses) in a dosing diary supplied by the site. If doses are missed or vomited or if an extra dose is taken, this must be indicated in the source documents and CRFs.

Patients experiencing toxicity may require treatment adjustment or discontinuation according to the guidelines specified in Table 2 and Table 4.

#### **5.4.4. Treatment After Initial Evidence of Radiologic Disease Progression in Both Arms**

Immunotherapeutic agents such as avelumab may produce anti-tumor effects by potentiating endogenous cancer-specific immune responses. The response patterns seen with such an approach may extend beyond the typical time course of responses seen with cytotoxic agents, and can manifest as a clinical response after an initial increase in tumor burden or even the appearance of new lesions.

If radiologic imaging shows disease progression as assessed by BICR, tumor assessment should be repeated at least  $\geq 4$  weeks later in absence of clinical deterioration in order to confirm disease progression. This confirmation of disease progression assessed by BICR will not affect the primary and secondary endpoints defined according to RECIST v.1.1.

Patients will receive study treatment while waiting for confirmation of PD in absence of clinical deterioration, as defined by the following criteria:

- Absence of clinical signs and symptoms (including worsening of laboratory values) of disease progression.
- No decline in ECOG performance status.
- Absence of rapid progression of disease by radiographic imaging.
- Absence of progressive tumor at critical anatomical sites (eg, cord compression) requiring urgent alternative medical intervention.

If repeat imaging no longer shows PD but rather CR, PR, or SD compared to the initial scan, treatment may be continued/resumed. In determining whether or not the tumor burden has increased or decreased, investigators should consider all target as well as non target lesions (refer to the Study Manual).

If the repeat imaging confirms PD by BICR assessment, patients should be discontinued from study treatment. However, according to the investigator's clinical judgment and after discussion between the investigator and the sponsor's medical monitor, if a patient with evidence of PD is still experiencing clinical benefit, the patient may be eligible for continued treatment with single-agent avelumab, single-agent axitinib, or avelumab in combination with axitinib in Arm A, or sunitinib monotherapy in Arm B (crossover between treatment arms is not permitted). The investigator's judgment should be based on the overall benefit-risk assessment and the patient's clinical condition, including performance status, clinical symptoms, adverse events and laboratory data.

In patients who continue treatment beyond progression by BICR assessment, the oncologic assessments should continue to be performed as per [SoA](#) and be recorded in the CRF until the study treatment is permanently discontinued.

Patients who stop avelumab after initial clinical benefit while on treatment and then experience radiologic disease progression confirmed by BICR thereafter will be eligible for re-treatment with avelumab at the discretion of the investigator and after discussion with the sponsor's medical monitor if 1) no cancer treatment was administered other than axitinib since the last dose of avelumab, 2) the patient does not meet the safety withdrawal criteria, and 3) the trial is still open.

After review of images by BICR is stopped following the final analyses for PFS performed as specified in the protocol ([Section 9.6](#)), permanent discontinuation of treatment will be performed as per investigator-assessed disease progression (see [Section 7.7](#)). After review of images by BICR is stopped, confirmation of disease progression  $\geq 4$  weeks after the PD was first noticed will no longer be required.

#### **5.4.5. Food Requirements**

All investigational products may be administered without regard to food but patients must avoid foods that are known strong CYP3A4/5 inhibitors (eg, grapefruit juice or grapefruit/grapefruit-related citrus fruits [eg, Seville oranges, pomelos]).

#### **5.4.6. Recommended Dose Modifications**

Every effort should be made to administer investigational product on the planned dose and schedule.

In the event of significant toxicity, dosing may be delayed and/or reduced as described below. In the event of multiple toxicities, dose modification should be based on the worst toxicity observed. Patients are to be instructed to notify investigators at the first occurrence of any adverse symptom. In addition to dose modifications, investigators are encouraged to employ best supportive care according to local institutional clinical practices and according to the guidance for selected adverse events provided below.

For axitinib and sunitinib, dose modifications may occur in 2 ways:

- Within a cycle: dosing interruption until adequate recovery and dose reduction, if required, during a given treatment cycle;
- In the next cycle: dose reduction may be required in a subsequent cycle based on toxicity experienced in the previous cycle.

For avelumab, no dose modifications are permitted in this study, but next infusion may be omitted based on persisting toxicity, as outlined in Table 3. Dose modifications of axitinib and infusion omissions of avelumab may occur independently for the two drugs and will be reported in the CRF.

Available axitinib and sunitinib dose levels for inpatient dose modification are listed in Table 1 and in Table 2, respectively.

##### **5.4.6.1. Inpatient Axitinib Dose Escalation and Dose Reduction**

Axitinib inpatient dose increase to 7 and/or 10 mg in combination with avelumab is prohibited in France, as per Agence nationale de sécurité du médicaments et de produits de santé (ANSM) request.

In other countries, inpatient axitinib dose escalation is permitted up to 10 mg BID and may occur according to the criteria described below.

Patients who tolerate the current axitinib dose without Grade >2 axitinib-related adverse events for 2 consecutive weeks have the option to have their axitinib dose increased (one dose level increase at a time) as indicated in Table 1 (unless the patient's BP is >150/90 mm Hg or the patient is receiving antihypertensive medication). Particular attention should be provided to a patient's overall safety profile prior to implementing inpatient axitinib dose escalation.

**Table 1. Axitinib Dose Levels**

Dose Level	Dose
+2	10 mg BID
+1	7 mg BID
Potential Starting Dose	5 mg BID
-1	3 mg BID
-2	2 mg BID

Patients will be monitored closely for toxicity, and axitinib treatment may be adjusted by dosing interruption with or without dose reduction as indicated in Table 3. Dosing interruption and/or dose reduction by 1, and if needed, 2 dose levels (one dose level decrease at a time) as indicated in Table 1 will be allowed depending on the type and severity of toxicity encountered. Management of patients requiring more than 2 dose reductions of axitinib (one dose level decrease at a time) should be discussed with the sponsor's medical monitor.

Patients who have undergone dose reduction may also undergo dose re-escalation back to the previous dose level at the discretion of the Investigator in the absence of Grade  $\geq 2$  non-hematologic treatment-related toxicity for at least 28 days.

#### **5.4.6.2. Sunitinib Dose Modifications**

Sunitinib dose interruptions and/or dose reduction by 1, and if needed 2 (one dose level decrease at a time), dose level(s) as indicated in Table 2 will be allowed depending on the type and severity of toxicity encountered provided that criteria for patient withdrawal in [Section 6.5](#) have not been met. If recovery to Grade  $\leq 1$  toxicity does not occur within 6 weeks, investigator should discuss with the medical monitor about any dose modification and or treatment continuation. Consult with the medical monitor before discontinuing the patient. No more than 2 dose reductions are permitted in any patient. If more than 2 dose reductions of sunitinib are required, further reductions should be discussed with the sponsor's medical monitor.

**Table 2. Sunitinib Dose Levels**

Dose Level	Dose
Starting Dose	50 mg QD
-1	37.5 mg QD
-2	25 mg QD

Sunitinib dose re-escalation back to the previous dose level is permitted in the absence of Grade  $\geq 3$  hematologic or Grade  $\geq 2$  non-hematologic treatment-related toxicity during the previous treatment cycle.

#### **5.4.6.3. Management of Axitinib- or Sunitinib-Related Hypertension**

Patients will be issued BP cuffs (provided by the sponsor) for home monitoring and instructed to measure their BP at least once daily (in Arm A before taking the morning dose of axitinib, and in Arm B before taking the daily dose of sunitinib during the 4 weeks of

treatment and any time during the day in the 2 weeks off treatment). All BP measurements will be recorded in a diary and brought to the nurse or study coordinator at each clinic visit. Patients should be instructed to contact the site immediately for guidance if their systolic blood pressure rises above 150 mm Hg, diastolic blood pressure rises above 100 mm Hg, or if they develop symptoms perceived to be related to elevated blood pressure (eg, headache, visual disturbances), although a different blood pressure threshold for contacting the site may be used according to the investigator's clinical judgment.

Blood pressure should be well-controlled prior to initiating therapy and patients should be monitored for hypertension. To treat an increase in BP, standard antihypertensives may be used (eg, thiazide or thiazide-like diuretics, angiotensin II receptor blockers, angiotensin converting-enzyme inhibitors, and calcium channel blockers, [except diltiazem since it is a strong CYP3A4 inhibitor], etc.).

For patients on sunitinib therapy, hypertension should be monitored and treated as needed with standard anti-hypertensive therapy.

Dose modifications for axitinib and sunitinib in case of hypertension are described in Table 3.

Post IA3, BP home monitoring will no longer be required.

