#### **5.4.6.4. Axitinib Dose Modifications, Avelumab Infusion Omissions, and Sunitinib Dose Modifications for Treatment-Related Toxicity**

In Arm A, recommended axitinib dose modifications and avelumab infusion omissions in case of drug related toxicity are shown in Table 3. The aforementioned guidelines might be further modified at the discretion of the sponsor based on the emerging safety profile of the combination. The investigator can consider consulting with the sponsor's medical monitor in case of persistent toxicity that would lead to dose modification or treatment discontinuation per toxicity treatment guidelines.

In Arm B, recommended sunitinib dose modifications in case of drug-related toxicity are shown in Table 4.

The 4-week sunitinib dosing period may not be extended to compensate for interruptions in sunitinib treatment due to any cause. If recovery to Grade  $\leq 1$  toxicity does not occur within 6 weeks, investigator should consider consulting with the medical monitor about any dose modification or treatment discontinuation.

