**Table 3. Axitinib Dose Modifications and Avelumab Infusion Omissions for Investigational Product-Related Toxicity**

Toxicity	NCI CTCAE Severity Grade	Axitinib	Avelumab
		Dose Modification	Treatment Modification
Hematologic Abnormalities	Grade 1	
 
Continue at the same dose level.
 
	
 
Continue as per schedule.
 

	Grade 2	
 
Continue at the same dose level.
 
	
 
Continue as per schedule.
 

	Grade 3	
 
Continue at the same dose level.
 
	
 
Withhold avelumab.
 
Re-initiate avelumab once toxicity is Grade <math>\leq 1</math> or baseline.
 
Permanently discontinue avelumab if toxicities does not resolve to Grade <math>\leq 1</math> or baseline within 12 weeks (consider consult with the medical monitor before permanently discontinuing the treatment).
 
 
Exceptions are: Laboratory values that do not have any clinical correlate.

	Grade 4	
 
Withhold until recovery to Grade <math>\leq 2</math>.
 
Then, reduce by 1 dose level and resume treatment.
 
For Grade 4 lymphopenia not associated with clinical events (eg, opportunistic infection) axitinib treatment may continue without interruption.
 
	
 
Permanently discontinue avelumab (consider consult with medical monitor before permanently discontinuing the treatment).
 
 
Exceptions are: Laboratory values that do not have any clinical correlate.

Proteinuria	Dipstick negative or shows 1+ (Grade 1)	
 
Continue at the same dose level.
 
	
 
Continue as per schedule.
 

	If dipstick shows >1+, perform 24 hour urine collection. Dosing may continue while waiting for test results		
	<2 g proteinuria/24 hour	
 
Continue at the same dose level.
 
	

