**Table 3. Axitinib Dose Modifications and Avelumab Infusion Omissions for Investigational Product-Related Toxicity**

Toxicity	NCI CTCAE Severity Grade	Axitinib	Avelumab
		Dose Modification	Treatment Modification
	2 systolic BP readings separated by at least 1 hour show systolic pressure >160 mm Hg OR 2 diastolic BP readings separated by at least 1 hour show diastolic pressure >105 mm Hg	
 
Withhold until BP is less than 150/100 mm Hg and adjust antihypertensive medication.
 
Then, reduce by 1 dose level and resume treatment.
 
 If axitinib dosing is temporarily discontinued, patients receiving antihypertensive medications should monitor closely for hypotension. The plasma half-life of axitinib is 2-4 hours and BP usually decreases within 1-2 days following dosing interruption.
 
See Section 5.4.6.3 for monitoring/management of axitinib-related hypertension.
 
	
 
Continue as per schedule.
 

	Recurrent hypertension following previous dose reduction (2 systolic BP readings separated by at least 1 hour show systolic pressure >150 mm Hg) OR Recurrent diastolic BP >100 mm Hg (2 BP readings separated by at least 1 hour) following previous dose reduction	
 
Repeat dose reduction by one lower dose level.
 
See Section 5.4.6.3 for monitoring/management of axitinib-related hypertension.
 
	
 
Continue as per schedule.
 

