**Table 4. Sunitinib Dose Modifications for Investigational Product Related Toxicity**

Toxicity	Grade 1/2	Grade 3 or intolerable Grade 2	Grade 4
Non-Hematologic (exceptions: CHF, pancreatitis, necrotizing fasciitis, nephrotic syndrome and thrombotic microangiopathy).***	Continue at the same dose level	Withhold dose until toxicity is Grade $\leq 1$ or has returned to baseline, then resume treatment at the same dose level.* If the toxicity recurs with Grade 3 severity (or intolerable Grade 2) at the discretion of the investigator, reduce the dose by 1 level.	Withhold dose until toxicity is Grade $\leq 1$ or has returned to baseline, then reduce the dose by 1 level and resume treatment, or discontinue at the discretion of the investigator.*
Hematologic	Continue at the same dose level	Withhold dose until toxicity is Grade $\leq 2$ or has returned to baseline, then resume treatment at the same dose level.** If the toxicity recurs with Grade 3 severity, at the discretion of the investigator, reduce the dose by 1 level.	Withhold dose until toxicity is Grade $\leq 2$ or has returned to baseline, then reduce the dose by 1 level and resume treatment.**
Left Ventricular Ejection Fraction Reduction.	Continue at the same dose level	The dose should be interrupted and/or reduced if without clinical evidence of CHF but with an ejection fraction $<50\%$ and $>20\%$ below baseline.	The dose should be interrupted and/or reduced if without clinical evidence of CHF but with an ejection fraction $<50\%$ and $>20\%$ below baseline.

\*Patients who develop Grade 4 hyperuricemia or Grade 3 hypophosphatemia without clinical symptoms may continue study treatment without interruption at the discretion of the Investigator. Nausea, vomiting, or diarrhea persist at Grade 3 or 4 despite maximal medical therapy.

\*\*Patients who develop Grade 3 or 4 lymphopenia may continue study treatment without interruption. Complicated neutropenia includes duration of Grade 4 longer than 7 days or concurrent fever or infection.

\*\*\*If occurs sunitinib should be discontinued.

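### Protocol 5.4.6.3 sends sunitinib hypertension dose changes to Table 3, which covers only axitinib and avelumab, while 5.4.3 and 5.4.6.4 send Arm B toxicity to Table 4

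*Protocol*

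**What the plan says.** The hypertension section, Protocol 5.4.6.3, says: "Dose modifications for axitinib and sunitinib in case of hypertension are described in Table 3". Its only other text specific to sunitinib hypertension management tells sites to monitor and to treat with standard antihypertensives, and gives no dose rule.

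Table 3 is titled "Axitinib Dose Modifications and Avelumab Infusion Omissions for Investigational Product-Related Toxicity". Section 5.4.6.4 ties it to one arm, "In Arm A, recommended axitinib dose modifications and avelumab infusion omissions in case of drug related toxicity are shown in Table 3", and ties the other arm to a different table: "In Arm B, recommended sunitinib dose modifications in case of drug-related toxicity are shown in Table 4". No exception is made for hypertension. Section 5.4.3, on sunitinib administration, likewise says that patients with toxicity may need adjustment or discontinuation "according to the guidelines specified in Table 2 and Table 4". It does not mention Table 3.

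In its upper blood-pressure tier, the axitinib column of Table 3 says "Withhold until BP is less than 150/100 mm Hg", followed by a one-level reduction on resumption. For a Grade 3 or intolerable Grade 2 non-hematologic event, Table 4 withholds sunitinib until Grade 1 or lower "or has returned to baseline, then resume treatment at the same dose level".

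On a different matter, Section 5.4.6.2 says "No more than 2 dose reductions are permitted in any patient". The next sentence provides for discussing further reductions with the medical monitor.

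**The concern.** The section a site would open for a hypertensive patient on sunitinib points to a table that contains no sunitinib instructions. Two other sections point to a table that contains sunitinib instructions but does not mention hypertension. A site that takes 5.4.6.3 at its word may apply axitinib's rows to sunitinib, and a site that follows 5.4.3 or 5.4.6.4 will use the generic row of Table 4. The same event in Arm B could then be handled in two ways.

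Hypertension is an expected sunitinib event: Protocol 1.2.2.3 gives 27.3% in pooled single-agent data. At stake are consistent handling of comparator patients and a clear reference standard for SAP summaries that depend on dosing: sunitinib dose intensity (6.5.3.3), reductions (6.5.3.4), interruptions (6.5.3.6) and incorrect-dose deviations (6.5.2.2).

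**Working it through.** There is no stated figure to reproduce. The check sets the passages side by side.

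**1. Table named for sunitinib toxicity**
- Section 5.4.3: Tables 2 and 4.
- Section 5.4.6.4: Table 4 for Arm B, Table 3 for Arm A.
- Section 5.4.6.3, hypertension only: Table 3.

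The two general sections agree with each other. The hypertension-specific section disagrees with both.

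**2. What Table 3 offers for sunitinib**
Nothing. On every page its columns are axitinib and avelumab. Its hypertension rows refer back to 5.4.6.3 for axitinib-related hypertension, and a note in the upper-tier row relies on axitinib's half-life of 2-4 hours. Section 1.2.2.3 gives about 40 and 80 hours for sunitinib and its active metabolite.

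**3. What Table 4 offers for hypertension**
No dedicated row. Hypertension is not among the listed exceptions to the non-hematologic row, so it falls under that row by default.

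**4. What happens if Table 3's rows are applied to sunitinib, as 5.4.6.3 directs**
- *Trigger.* Table 3 uses two readings at least an hour apart against mm Hg thresholds. The non-hematologic row of Table 4 uses grade.
- *Above 150 systolic or 100 diastolic.* Table 3 adds an antihypertensive and keeps the dose, or reduces one level if antihypertensive treatment is already maximal. Table 4 keeps the dose for Grade 1/2 but withholds for Grade 3 or intolerable Grade 2.
- *Above 160 systolic or 105 diastolic.* Table 3 withholds, then resumes one level lower. Table 4, after a first Grade 3 or intolerable Grade 2 event, resumes at the same level. For a patient at the starting dose, the Table 2 levels would be 37.5 mg under one reading and 50 mg under the other. This holds only if the same event meets both conditions.
- *Grade 4.* Table 4 withholds, then reduces one level or discontinues. The first option matches Table 3's upper tier.
- *Recurrence.* Table 3 repeats the reduction when hypertension recurs after an earlier one. Table 4 reduces one level at the investigator's discretion.

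Divergence can go either way. For an event between the two thresholds that is also Grade 3, in a patient not on maximal antihypertensives, Table 4 withholds where Table 3 continues.

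**5. Frequency**
The documents do not map the mm Hg thresholds to grades, so the number of diverging cases cannot be derived. As context only: assuming that the pooled 27.3% (mixed solid tumors, any cause) held in Arm B, and that Arm B is half of 830, 0.273 × 415 ≈ 113 patients would have hypertension of some severity. An unknown part of these would reach a point where the tables differ.

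**6. Section 5.4.6.2**
Table 2 lists two levels below the starting dose, which fits a limit of two reductions. The next sentence then opens a route to more. The parallel axitinib text in 5.4.6.1 has the discussion route without the prohibition.

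**The case against.** The strongest reply is that this is one stray table number. Section 5.4.3, Section 5.4.6.4 and both table titles point to Table 4 for sunitinib, and Table 3's hypertension rows are plainly written for axitinib. A careful reader would probably land on Table 4. That largely stands. It rules out the tempting inference that the protocol leaves the choice entirely open, or that it contains two fully specified comparator regimens in conflict. The clash of actions appears only when axitinib rows are carried over to sunitinib. It does not dispose of the point, because the sentence that tells sites to look in Table 3 is the one written for hypertension, and no text ranks it below the general sections.

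Further mitigations also stand. Section 5.4.6.4 calls the modifications recommended, Table 4 leaves several steps to the investigator, and medical monitor consultation is available. Table 2's note permits re-escalation, so a dose difference need not persist. This protocol version already has a schedule for after the 28-Apr-2020 IA3 cut-off, so a correction reaches only patients still on sunitinib, whose number is not given.

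The two sentences in 5.4.6.2 can be read as a default cap with exceptions by discussion. That reading is possible but is not what the first sentence says. The issue is separate and adds no weight to the hypertension point.

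**Conclusion.** The point holds as an internal inconsistency in operative dosing text. Section 5.4.6.3 refers sunitinib hypertension to a table without sunitinib content, against Sections 5.4.3 and 5.4.6.4, and the table those sections name has no hypertension row. This follows from the text alone.

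The size is limited and partly unknown. The 37.5 mg against 50 mg contrast is one conditional case: it needs Table 3's upper axitinib tier to be applied to sunitinib for an event that is also a first Grade 3 or intolerable Grade 2 event under Table 4. It does not describe severe hypertension in general.

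A reader might also infer that the control arm was dosed unfairly or that the efficacy comparison is biased. The documents do not support that: they give no frequency, no consistent direction and no link to outcome. Alpha, power, event counts and boundaries are unaffected. The analysis consequence is narrower: until the passages agree, incorrect-dose deviations for Arm B hypertension have no single standard to be judged against.

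The wording in 5.4.6.2 on more than two reductions is a lesser, separate inconsistency.

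**What to change.** The sponsor should reconcile Protocol Sections 5.4.3, 5.4.6.3 and 5.4.6.4 with Tables 3 and 4, so that one stated rule applies to sunitinib-related hypertension and every cross-reference leads to it. Separately, the two consecutive sentences in Section 5.4.6.2 on the number of sunitinib reductions should be made consistent. Which rule applies in either case is for the sponsor to decide; none is proposed here.

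The cost is protocol wording and the usual amendment and site communication. No change to sample size, testing strategy or the SAP's efficacy methods is needed.
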